Summary Table of Study Protocol

Title	Observational Serial Chart Review of Repatha® Use in European Subjects With Hyperlipidaemia
Protocol version identifier	Amendment 2
Date of last version of the protocol	13 February 2018
EU Post Authorisation Study (PAS) Register No	EUPAS13328
Active Substance	Evolocumab
Medicinal Product	Repatha®
Product Reference	EU/1/15/1016
Procedure Number	EMA/H/C/3766
NCT Number	NCT02770131
Marketing Authorisation Holder(s)	Amgen Europe B.V.
Joint PASS	NA
Research Question and Objectives	
Research Question: What are the clinical characteristics of patients who are prescribed Repatha® in the post-launch period, and how is their treatment managed?
 
Primary Objective: To describe the clinical characteristics of subjects at initiation of Repatha®
 
Secondary Objective: To describe parameters associated with clinical management of hyperlipidaemia, in subjects initiated on Repatha® treatment

Countries of Study	Multiple countries across Europe
Author	PPD Amgen Ltd [name]

Marketing Authorisation Holder

Marketing authorisation holder(s)	Amgen Europe B.V.
MAH Contact	PPD Amgen Ltd [name] PPD

Confidentiality Notice

This document contains confidential information of Amgen Inc.

This document must not be disclosed to anyone other than the site study staff and members of the Institutional Review Board/Independent Ethics Committee/Institutional Scientific Review Board or equivalent, as applicable.

The information in this document cannot be used for any purpose other than the evaluation or conduct of the research without the prior written consent of Amgen Inc.

If you have questions regarding how this document may be used or shared, call the Amgen Medical Information number: [name] (toll-free) or [name]

Investigator's Agreement

I have read the attached protocol entitled "Observational Serial Chart Review of Repatha® Use in European Subjects with Hyperlipidaemia", dated **20 December 2018**, and agree to abide by all provisions set forth therein.

[figure not shown]
I agree to ensure that the confidential information contained in this document will not be used for any purpose other than the evaluation or conduct of the clinical investigation without the prior written consent of Amgen Inc.

Signature

Name of Investigator

Date (DD Month YYYY)

Study Design Schema

- Enrolment occurs only after initiation of Repatha® at physician discretion, independent of study protocol
- Where enrolment into study occurs after Repatha® initiation; all relevant follow-up data between Repatha® initiation and prior to study enrolment will be captured in a retrospective manner
- Calendar time for enrolment period at a country level is dependent on launch in each country; the enrolment period for the study on the whole is anticipated to span from Q1 2016 to Q4 2018
- Follow-up at the individual subject level continues for up to 30 months from start of Repatha® treatment irrespective of whether subject continues to receive Repatha®

1. Table of Contents

Summary Table of Study Protocol	1
Study Design Schema.....	5
1. Table of Contents.....	6
2. List of Abbreviations.....	9
3. Responsible Parties	10
4. Abstract.....	10
5. Amendments and Updates.....	14
6. Milestones	15
7. Rationale and Background.....	15
7.1 Diseases and Therapeutic Area	15
7.2 Rationale	16
7.3 Statistical Inference (Hypothesis).....	17
8. Research Question and Objectives.....	17
8.1 Primary Objective	17
8.2 Secondary Objectives.....	17
8.3 Exploratory Objective	17
9. Research Methods	17
9.1 Study Design	17
9.2 Setting and Study Population	18
9.2.1 Study Period.....	18
9.2.2 Selection and Number of Sites.....	18
9.2.3 Subject Eligibility.....	18
9.2.3.1 Inclusion Criteria	18
9.2.3.2 Exclusion Criteria	18
9.2.4 Matching.....	19
9.2.5 Baseline Period	19
9.2.6 Study Follow-up.....	19
9.3 Variables.....	19
9.3.1 Exposure Assessment.....	19
9.3.2 Outcome Assessment	19
9.3.2.1 Primary Outcome	19
9.3.2.2 Secondary Outcomes	20
9.3.2.3 Exploratory Outcome	21
9.3.3 Covariate Assessment.....	21
9.3.4 Validity and Reliability.....	21
9.4 Data Sources.....	21

9.5	Study Size	21
9.6	Data Management	23
9.6.1	Obtaining Data Files	24
9.6.2	Linking Data Files	24
9.6.3	Review and Verification of Data Quality	24
9.7	Data Analysis.....	24
9.7.1	Planned Analyses.....	24
9.7.1.1	Interim Analyses	24
9.7.1.2	Primary Analysis	24
9.7.2	Planned Method of Analysis	24
9.7.2.1	General Considerations	25
9.7.2.2	Missing or Incomplete Data and Lost to Follow-up	25
9.7.2.3	Descriptive Analysis.....	26
9.7.2.4	Analysis of the Primary, Secondary and Exploratory Endpoints.....	27
9.7.2.5	Sensitivity Analysis	27
9.7.3	Analysis of Safety Endpoint(s)/Outcome(s).....	28
9.8	Quality Control.....	28
9.9	Limitations of the Research Methods	29
9.9.1	Internal Validity of Study Design.....	29

Persistence	Individual subject time on therapy
SOP	Standard Operating Procedure
Source data	Information from an original record or certified as a copy of the original record containing patient information for use in clinical research. The information may include, but is not limited to, clinical findings, observations or other activities in a study necessary for the reconstruction and evaluation of the study. Source data are contained in source documents (original records or certified copies). (ICH Guideline E6).
Study start	Date on which data for first enrolled subject is first entered into EDC
WHO	World Health Organisation

3. Responsible Parties

Amgen Ltd is responsible for all aspects of study execution, conduct and reporting.

4. Abstract

- Study Title: Observational Serial Chart Review of Repatha® Use in European Subjects with Hyperlipidaemia
- Study Background and Rationale:

Cardiovascular disease (CVD) represents the leading cause of death and disability in the world, comprising over 10% of the global total disease burden. In 2008, the World Health Organization (WHO) reported that CVD accounted for over 17 million deaths, nearly 80% of which were due to heart attacks and strokes alone.

Elevated cholesterol is among the leading risk factors for cardiovascular deaths, with an estimated prevalence of 39% globally among all adults (greater in high-income countries). It is estimated that up to 50% of the European population aged 35-64 years has a total cholesterol > 6.5 mmol/L (Tolonen et al, 2005), (equivalent to > 254 mg/dL). This high prevalence of dyslipidemia translates into significant cardiovascular morbidity and mortality.

Over 50 million patients in the United States, Europe, and Japan are currently treated with lipid lowering therapies (LLTs). The rationale for treatment of dyslipidemia derives from extensive clinical trial data which demonstrate that the reduction in total cholesterol, non-high density lipoprotein-C (HDL-C), and most importantly, low density lipoprotein-C (LDL-C) through pharmacological therapies lowers the risk of CVD events (Kannel et al, 1974; Kannel, 1995; Kannel et al, 1979). A recent Cholesterol Treatment Trialists' (CTT) Collaboration (CTT et al, 2010) meta-analysis which included 21 randomized controlled trials involving nearly 170,000 patients showed that for every 1 mmol/L (equivalent to 39 mg/dL) reduction of LDL-C there was a 20% reduction in the risk of major vascular events (coronary death, non-fatal myocardial infarction, coronary revascularisation, or stroke).

A serine protease expressed predominantly in the liver, kidney and intestine (Seidah, 2003), proprotein convertase subtilisin/kexin type 9 (PCSK9), plays an important role in the recycling and regulation of the LDL receptor (Horton et al, 2007; Brown and Goldstein, 2006). PCSK9 acts via direct binding to the LDL receptor, resulting in post-translational down-regulation of receptor expression on the hepatic cell surface. This in turn leads to increased levels of circulating LDL-C. Repatha® (evolocumab) is a fully human monoclonal immunoglobulin (Ig) G2 that binds specifically

to human PCSK9. Following parenteral administration, it inhibits circulating PCSK9 from binding to the low-density lipoprotein receptor (LDLR) on the liver cell surface, thus preventing PCSK9-mediated LDLR degradation. It increases liver LDLR levels resulting in associated reductions in serum LDL-C.

Repatha® is indicated in adults with primary hypercholesterolaemia (heterozygous familial and non-familial) or mixed dyslipidaemia, as an adjunct to diet, in combination with a statin or statin with other lipid-lowering therapies in patients unable to reach LDL C goals with the maximum tolerated dose of a statin or, alone or in combination with other lipid-lowering therapies in patients who are statin-intolerant, or for whom a statin is contraindicated. ([Repatha® EPAR](#))

European Medicines Agency (EMA) approval for Repatha® was granted on 17th July 2015. The data submitted in support of the filing were generated from an extensive interventional clinical trial programme in which selected populations were enrolled and managed according to strictly-defined protocols in a controlled setting. More recently, the 27,564 patient FOURIER trial which evaluated the effect of lowering LDL-C with evolocumab in subjects with established atherosclerotic disease reported a 20% relative risk reduction in major adverse cardiac events compared to those on optimized oral lipid lowering therapy ([Sabatine et al, 2017](#)). However such data can not necessarily be generalised to routine clinical practice especially given the varying reimbursement rules and availability of the drug in participating countries, and at present there is little information describing Repatha® use in a real-world setting.

Across Europe, country health authorities grant local access approvals based on clinical trial data; it is recognised that local conditions may limit the population eligible to receive Repatha® through application of criteria other than the terms of the label. As the next step, real world evidence describing product use in routine clinical practice is required, for continuation and/or reassessment of access.

The design and objectives of this study address the requests being made by the health authorities. In particular, authorities require local real-world data on the patient population which is receiving Repatha®, including patient characteristics, dosing patterns and effectiveness in lowering LDL-C. The study will be conducted only in countries which require real world data to be collected in the post-launch setting and where it is allowed as per local regulations to study the use of a single treatment in clinical practice.

Data obtained from this study are intended to fulfil health authorities' requirements and to provide a robust source of published information for physicians.

- Research Question and Objectives
 - Primary Objective:
To describe the clinical characteristics of subjects at initiation of Repatha®
 - Secondary Objectives are to describe the following:
 - LDL-C and other cholesterol values over time
 - Repatha® use over time (dose, dose frequency)
 - Use of other lipid-modifying therapies (LMTs) over time (type, dose, dose frequency)
 - Physician visits (dates and reason)
 - Hospitalisation (dates and reason)
- Hypothesis

No formal hypothesis will be tested in this observational study

- Study Design/Type

Observational cohort study collecting data through serial chart review

- Study Population

The study population comprises patients from European countries, who have received Repatha® as part of routine clinical management of their hyperlipidaemia, between August 2015 and June 2021.

- Summary of Subject Eligibility Criteria
 - All inclusion criteria need to be met, as follows:
 - Adults (\geq 18 years)
 - Provided informed consent if applicable according to local requirements
 - Initiated on Repatha® at physician's discretion, after 1st August 2015
 - Received at least one dose of Repatha®
 - If at least one exclusion criterion is met, subject is not eligible for participation in the study, as follows:
 - Enrolled in an interventional study of PCSK9 inhibitor within 12 weeks prior to initiation of Repatha®
 - Received commercially available PCSK9 inhibitor within 12 weeks prior to initiation of Repatha®
- Follow-up

Individual observation period is up to 36 months; capture of baseline data from up to 6 months prior to the date of initiation of Repatha® and a maximum of 30 months of follow-up data after the date of Repatha® initiation.

The study period is expected to extend from 1st August 2015 to 30 June 2021.

- Variables

Outcome Variables:

Baseline period

- Demographics: age (at initiation of Repatha®), gender, country
- Cardiovascular risk factors, including body mass index (BMI), smoking status, vascular bed involvement, chronic kidney disease status (CKD), history of hypertension (see also [Appendix B](#))
- Familial hypercholesterolaemia (FH) status
- Diabetic status including type 1 or 2, and HbA1C (closest to initiation of Repatha®)
- Cardiovascular history (see [Appendix B](#) for list of applicable conditions/events)
- Cholesterol values including total cholesterol, LDL-C, HDL-C, non-HDL-C, triglycerides
- Dose, dose frequency, commencement date of Repatha® administration
- Type, dose, dose frequency, commencement and discontinuation dates of other LMT administration including apheresis
- History of statin intolerance (y,n)
- Dates and reason for hospital admittance/final diagnosis
- Dates of physician visits and reason for attendance

Follow-up period

- Cholesterol values including total cholesterol, LDL-C, HDL-C, non-HDL-C, triglycerides
- Dose, dose frequency, commencement and discontinuation dates of Repatha® administration
- Type, dose, dose frequency, commencement and discontinuation dates of other LMT administration including apheresis
- Dates and reason for hospital admittance/final diagnosis
- Dates of physician visits and reason for attendance
- Medication persistence
- Medication adherence

End of study

- Date of last Repatha® dose
- Reason for cessation of Repatha® therapy, if stopped within the observation period
- Primary reason for ending study
- Study Sample Size

The primary outcome measures for the study involve estimating the percentage of subjects with clinical characteristics of interest (FH, diabetes, CV history) and also estimating the baseline LDL-C levels. The intention is to perform the analyses by country. The planned sample size for the study is 2000 subjects across approximately 15 countries; an average of approximately 130 subjects per country.

The sample size is expected to enable precise estimates of the primary outcome measures to be obtained for each participating country.

- Data Analysis

All summaries of the data will be descriptive in nature. For categorical variables the frequency and percentage, with 95% confidence interval, will be given.

Summary statistics for continuous variables will include the number of subjects, mean, median, standard deviation or standard error, 25th percentile (Q1), 75th percentile (Q3), minimum, and maximum.

5. Amendments and Updates

Amendment or Update No.	Date	Section of Study Protocol	Amendment or Update	Reason
1	13 Feb 2018		See summary of changes	
2	20 December 2018		See summary of changes	

6. Milestones

Milestone	Planned date
Start of data collection	April 2016
Interim analysis 1	March 2017
Interim analysis 2	June 2017
Interim analysis 3	August 2017
Interim analysis 4	November 2017
Interim analysis 5	Q2 2018
Interim analysis 6	2019
Interim analysis 7	2020
End of data collection	June 2021
Final report of study results	Dec 2021

7. Rationale and Background

7.1 Diseases and Therapeutic Area

Cardiovascular disease (CVD) represents the leading cause of death and disability in the world, comprising over 10% of the global total disease burden. In 2008, the World Health Organization (WHO) reported that CVD accounted for over 17 million deaths, nearly 80% of which were due to heart attacks and strokes alone.

Elevated cholesterol is among the leading risk factors for cardiovascular deaths, with an estimated prevalence of 39% globally among all adults (greater in high-income countries). It is estimated that up to 50% of the European population aged 35-64 years has a total cholesterol > 6.5 mmol/L ([Tolonen et al, 2005](#)) (equivalent to > 254 mg/dL). This high prevalence of dyslipidemia translates into significant cardiovascular morbidity and mortality.

Over 50 million patients in the US, Europe, and Japan are currently treated with lipid lowering therapies (LLTs). The rationale for treatment of dyslipidemia derives from extensive clinical trial data which demonstrate that the reduction in total cholesterol, non-HDL-C, and most importantly, LDL-C through pharmacological therapies lowers the risk of CVD events ([Kannel et al, 1974](#); [Kannel, 1995](#); [Kannel et al, 1979](#)). A recent Cholesterol Treatment Trialists' (CTT) Collaboration ([CTT et al, 2010](#)) meta-analysis which included 21 randomized controlled trials involving nearly 170,000 patients showed that for every 1 mmol/L (equivalent to 39 mg/dL) reduction of LDL-C there was a 20% reduction in the risk of major vascular events (coronary death, non-fatal myocardial infarction, coronary revascularisation, or stroke).

Repatha® (evolocumab) is a fully human monoclonal IgG2 antibody directed against proprotein convertase subtilisin/kexin type 9 (PCSK9). Following parenteral administration, it inhibits circulating PCSK9 from binding to the low-density lipoprotein receptor (LDLR) on the liver cell surface, thus preventing PCSK9-mediated LDLR degradation. It increases liver LDLR levels resulting in associated reductions in serum LDL-C.

Repatha® is indicated in adults with primary hypercholesterolaemia (heterozygous familial and non familial) or mixed dyslipidaemia, as an adjunct to diet, in combination with a statin or statin with other lipid-lowering therapies in patients unable to reach LDL C goals with the maximum tolerated dose of a statin or, alone or in combination with other lipid-lowering therapies in patients who are statin-intolerant, or for whom a statin is contraindicated.

7.2 Rationale

EMA approval for Repatha® was granted on 17th July 2015. The data submitted in support of the filing were generated from an extensive interventional clinical trial programme in which selected populations were enrolled and managed according to strictly-defined protocols in a controlled setting. More recently, the 27,564 patient FOURIER trial which evaluated the effect of lowering LDL-C with evolocumab in subjects with established atherosclerotic disease reported a 20% relative risk reduction in major adverse cardiac events compared to those on optimized oral lipid lowering therapy ([Sabatine et al, 2017](#)). However, such data can not necessarily be generalised to routine clinical practice especially given the varying reimbursement rules and availability of the drug in participating countries, and at present there is little information describing Repatha® use in a real-world setting.

Across Europe, country health authorities grant local access approvals based on clinical trial data. As the next step, real world evidence describing product use in routine clinical practice are required, for continuation and/or reassessment of access. The design and objectives of this study address the anticipated requests being made by the health authorities. In particular, authorities require local real-world data on the patient population which is receiving Repatha®, including patient characteristics, dosing patterns and effectiveness in lowering LDL-C. The study will be conducted only in countries which require real world data to be collected in the post-launch setting and where it is allowed as per local regulations to study the use of a single treatment in clinical practice.

Data obtained from this study are intended to fulfil health authorities' requirements and to provide a robust source of published information for physicians.

7.3 Statistical Inference (Hypothesis)

No formal hypothesis will be tested in this observational study. The study aims to describe the characteristics of subjects who commence treatment with Repatha®. The sample size is expected to enable sufficiently precise estimates of the primary outcome measures to be obtained for each participating country.

8. Research Question and Objectives

Research Question: What are the clinical characteristics of patients prescribed Repatha® in the post-launch period, and how is their treatment managed?

8.1 Primary Objective

To describe the clinical characteristics of subjects at initiation of Repatha®

8.2 Secondary Objectives

- To describe LDL-C and other cholesterol concentrations over time
- To describe treatment patterns of use of Repatha® over time
- To describe treatment patterns of use of other lipid modifying therapies over time
- To describe Health Resource Utilisation components, including hospitalisations and physician visits

8.3 Exploratory Objective

To evaluate incidence of LDL-C below 50 mg/dL (below 1.3 mmol/L)

9. Research Methods

9.1 Study Design

This cohort study is a multicountry, observational, serial chart review study of European patients receiving Repatha® as part of routine clinical management of their hyperlipidaemia. It is designed to capture data on clinical parameters relevant to health authorities and physicians.

Following approval of Repatha®, which was granted after review of data from an extensive interventional clinical trial programme, health authorities and other bodies now require real-world evidence on the clinical profile of patients who receive Repatha® in the immediate post-launch period, hence a non-interventional design is essential.

Enrolment will not be stratified by population characteristics, although a cap will be placed on total enrolment per country.

This study protocol is for a non-interventional, observational study and does not alter the clinical management of patients.

9.2 Setting and Study Population

9.2.1 Study Period

At the individual subject level, data will be captured for up to 36 months (up to 6 months pre-initiation of Repatha® and up to 30 months follow-up post-initiation of Repatha®).

At the study level, data will be captured for the periods spanning February 2015 (includes the 6-month period prior to the earliest possible prescription of commercial Repatha®) and June 2021.

9.2.2 Selection and Number of Sites

Sites in Europe where patients are being treated with commercially available Repatha® will be considered for inclusion. These are anticipated to be specialist sites which treat patients at high or very high risk of experiencing a CV event, including but not limited to FH patients.

Potential sites will be identified, approached and selection confirmed according to Amgen standard operating procedures (SOPs); selection is based on interest in participation as a study site, willingness and ability to comply with the protocol and data entry conventions, and agreement to follow the subjects throughout the observation period.

9.2.3 Subject Eligibility

9.2.3.1 Inclusion Criteria

All inclusion criteria need to be met, as follows:

- Adults (\geq 18 years)
- Provided informed consent if applicable according to local requirements
- Initiated on Repatha® at physician's discretion, after 1st August 2015
- Received at least one dose of Repatha®

9.2.3.2 Exclusion Criteria

If at least one exclusion criterion is met, subject is not eligible for participation in the study, as follows:

- Enrolled in an interventional study of PCSK9 inhibitor within 12 weeks prior to initiation of Repatha®
- Received commercially available PCSK9 inhibitor within 12 weeks prior to initiation of Repatha®

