9.2.5 Baseline Period

The baseline period is from the 6 months prior to the first dose of Repatha® through to the date of administration of the first dose of Repatha®. Therefore, the end of the baseline period coincides with the first dose of Repatha®.

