9.3.2.1 Primary Outcome

Clinical characteristics at time of initiation of Repatha® as assessed in relation to:

- FH status (diagnosed/not diagnosed)
- CV history (see [Appendix B](#) for a list of diagnoses/events)

- Diabetic status (diabetic/not diabetic; Type 1 or Type II; HbA1C measurement closest to initiation of Repatha®)
- Cholesterol values including total cholesterol, LDL-C, HDL-C, non-HDL-C, triglycerides (value(s) available in the 26-week baseline period)
- Demographics (age at initiation of Repatha®, gender, country)
- Cardiovascular risk factors (body mass index (BMI), smoking status, chronic kidney disease, history of hypertension, vascular bed involvement (see also [Appendix B](#)))
- History of statin intolerance (y,n)
- Dose, dose frequency, commencement date of Repatha® administration
- Type, dose, dose frequency, commencement and discontinuation dates of other LMT administration including apheresis
- Dates and reason for hospital admittance/final diagnosis
- Dates of physician visits and reason for attendance

Of note, LMT use (including apheresis) over the 6 months prior to initiation of Repatha® will be summarised and the regimen in place at the time of Repatha® initiation will be regarded as the baseline.

In addition, LDL-C and other relevant lipid panel measurements and HbA1C as assessed within 6 months prior to initiation of Repatha® (or the mean of the two most recent LDL-C measurements, if there is more than one) will be regarded as the respective baseline values.

All CV history and diabetic status will be reported as baseline data

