9.7.2 Planned Method of Analysis

All summaries of the data will be descriptive in nature. For categorical variables the frequency and percentage, with 95% confidence interval, will be given.

Summary statistics for continuous variables will include the number of subjects, mean, median, standard deviation or standard error, 25th percentile (Q1), 75th percentile (Q3), minimum, and maximum.

For the outcome measure of LDL-C and other cholesterol values over time, the data collection period (up to 6 months pre-initiation of Repatha® and up to 30 months post-initiation of Repatha®) will be divided into time windows. For each subject the mean LDL-C and other cholesterol values during each time period will be obtained, and summary statistics will be produced based on these mean values. In order to optimally utilize the available LDL-C and other cholesterol data, the following time windows will be used:

Definition 1: Period of 6 months duration pre-initiation of Repatha® (to obtain baseline LDL-C), windows of 3 months duration post initiation of Repatha® (months 1-3, months 4-6, months 7-9 and so on, through months 28-30)

Definition 2: Period of 6 months duration pre-initiation of Repatha® (to obtain baseline LDL-C), windows of 6 months duration post initiation of Repatha® (months 1-6, months 7-12, months 13-18 and so on through months 25-30)

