9.9 Limitations of the Research Methods

9.9.1 Internal Validity of Study Design

9.9.1.1 Information Bias

For the primary objective, information bias is not anticipated to be applicable, as Investigators will be aware of the subjects' age and gender, and will have paid particular attention to their CV history as they have been referred for CV cause. It is possible that lipids may be measured more frequently in very high risk and/or sicker patients, which could influence the baseline LDL-C; to help prevent this, a maximum of two LDL-C values in the 6 months prior to initiation of Repatha® will be considered for inclusion in the baseline, and these will be the two most recent values prior to the initiation date.

For the secondary objectives, it is expected that Investigators will follow all subjects closely as: 1. they have been initiated on a novel therapeutic in the immediate post-launch period. LDL-C values and use of Repatha® and any concomitant medications will be significant markers of clinical care, and are likely to be assessed on an ongoing basis over the observation period. 2. Subjects are high risk patients in secondary care.

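### The PCSK9-inhibitor exclusion covers 12 weeks but the baseline LDL-C window covers 26, so some on-drug values can lower the primary baseline mean

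*Protocol*

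**What the plan says.** Two exclusions in Protocol section 9.2.3.2 concern earlier exposure to the drug class. One removes a subject who "Received commercially available PCSK9 inhibitor within 12 weeks prior to initiation of Repatha". The other removes a subject who was "Enrolled in an interventional study of PCSK9 inhibitor within 12 weeks prior to initiation of Repatha".

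The baseline window is longer. Section 9.2.5 states: "The baseline period is from the 6 months prior to the first dose of Repatha® through to the date of administration" of the first dose. Section 9.3.2.1 lists the lipid panel with "value(s) available in the 26-week baseline period" and fixes the derivation: a value from the 6 months before initiation ("or the mean of the two most recent LDL-C measurements, if there is more than one) will be regarded as the respective baseline values"). Section 9.9.1.1 repeats the limit on number: "a maximum of two LDL-C values in the 6 months prior to initiation of Repatha® will be considered for inclusion in the baseline". The reason given there is that sicker patients may be measured more often. Earlier PCSK9-inhibitor use is not mentioned.

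Section 9.7.2, on lipids over time, averages all of a subject's values within each window. The pre-treatment window is described as "Period of 6 months duration pre-initiation of Repatha® (to obtain baseline LDL-C").

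No section removes lipid values measured while a subject was on another PCSK9 inhibitor.

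**The concern.** Eligibility and the baseline rule are both fixed in the Protocol, and they do not fit together. A subject may have been on a PCSK9 inhibitor in the earlier part of the same 6 months from which baseline LDL-C is taken. The Protocol's own background sections (4 and 7.1) say that this mechanism lowers LDL-C, so any error is downward.

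Section 9.5 names the mean LDL-C before initiation as the continuous primary outcome measure, to be estimated by country. The same variable defines a median-split subgroup in section 9.7.2.5.1, and it is the natural starting point for reading the LDL-C course after initiation. A shift of this kind does not shrink as the sample grows.

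The study-participation criterion could widen the gap. If it refers to the date of joining a study, a participant who joined a long study a year earlier and left last week passes it. The other criterion would not catch that person, because it covers only marketed product.

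**Working it through.** **Inputs from the Protocol.** Exclusion interval 12 weeks (9.2.3.2). Baseline window 26 weeks, at most the two latest LDL-C values (9.3.2.1, 9.9.1.1). About 130 subjects per country, SD 40 to 55 mg/dL, 95% confidence (9.5).

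**Inputs that are assumptions.** The share of a country's subjects affected, f, from 1% to 10%. The LDL-C lowering on the earlier drug, D, from 40 to 80 mg/dL. The Protocol gives neither.

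**Step 1: the plan's own figure.** Half-width = 1.96 × SD / √N. With SD 50 and N = 130 this is 98 / 11.40 = 8.60 mg/dL, as stated. All 16 cells of the table in 9.5 reproduce to within 0.01 mg/dL. The 35% example gives 1.96 × √(0.35 × 0.65 / 130) = 8.2%, stated as about 8%.

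**Step 2: the uncovered span.** 26 − 12 = 14 weeks, or 14/26 = 54% of the window. This is the maximum. A subject who stopped 20 weeks before initiation has on-drug values only in the 6 weeks from −26 to −20, plus the time the effect takes to wear off.

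**Step 3: the weight w of on-drug values in one subject's baseline.**
- Two or more later off-drug values: w = 0.
- One later off-drug value plus one on-drug value: w = 0.5.
- No later off-drug value: w = 1.

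**Step 4: the shift in a country mean.** Shift = −f × w × D, shown for w = 0.5 to w = 1, in mg/dL:

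| D | f = 1% | f = 5% | f = 10% |
|---|---|---|---|
| 40 | −0.2 to −0.4 | −1.0 to −2.0 | −2.0 to −4.0 |
| 60 | −0.3 to −0.6 | −1.5 to −3.0 | −3.0 to −6.0 |
| 80 | −0.4 to −0.8 | −2.0 to −4.0 | −4.0 to −8.0 |

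**Step 5: what it would take to equal the half-width.** f = 8.60 / (w × D). At D = 60 this is 8.60/60 = 14% (about 19 of 130) with w = 1, and 8.60/30 = 29% (about 37 of 130) with w = 0.5.

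**Step 6: the study-participation criterion.** Read as participation at any time in the 12 weeks, it leaves the same gap as the marketed-product criterion. Read as the enrolment date, it lets in a subject dosed until shortly before initiation. That subject's most recent values are on-drug, so w can be 1 even with two recent measurements.

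**The case against.** The best defence is that the rule limiting baseline to the two latest values already does most of the work. Anyone eligible under the marketed-product criterion has been off drug for at least 12 weeks. If two LDL-C values were taken after the effect wore off, nothing is wrong. Contamination needs a stop in a narrow interval, a new start on Repatha, and sparse later measurement. In the immediate post-launch period few patients may fit. This stands, and it is why the likely size is small. It does not close the gap: section 9.7.2.2 accepts that laboratory measurement may be infrequent, and no limit is set on the age of a value within the 6 months.

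Three stronger readings are tempting, and the Protocol does not support them.
- A reader might infer from section 9.7.2 that every on-drug value in the window enters the primary baseline. That averaging rule is introduced for lipids over time, while 9.3.2.1 and 9.9.1.1 define the baseline value. It would admit such values more easily only if it were used for baseline.
- A reader might infer that the bias overwhelms the planned precision. With f and D both assumed, most scenarios fall well short of 8.60 mg/dL.
- For lipid-modifying therapy, "the regimen in place at the time of Repatha® initiation will be regarded as the baseline", and a reader might infer that baseline LDL-C must be matched to that regimen. The Protocol does not promise this. Such a rule would redefine the primary outcome for anyone whose therapy changed in the 6 months, which is a trade-off and not a correction.

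It is also fair that the participation criterion can equally mean being in a study during those weeks, that no change-from-baseline outcome is defined, and that a derivation detail of this kind may sit in an SAP that is not shown. Even so, the Protocol states its own baseline rule, and followed as written that rule admits on-drug values.

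**Conclusion.** The point holds in a narrow form. The 12-week exclusion and the 26-week baseline window let an eligible subject with fewer than two later off-drug values contribute an on-drug LDL-C to the primary baseline mean. The direction is downward. Under the assumed ranges (40 to 80 mg/dL lowering, 1% to 10% affected) a country mean shifts by about 0.2 to 8 mg/dL. With 5% affected and 60 mg/dL lowering it shifts by 1.5 to 3.0 mg/dL, about 17% to 35% of the 8.60 half-width. The top of the range needs 10% affected, 80 mg/dL lowering and no off-drug value in any affected subject. It stays below 8.60 but would exceed the smallest half-width in the section 9.5 table, 6.40 (SD 40, N = 150).

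Only the LDL-C and other lipid parts of the primary outcome are touched. FH status, CV history and diabetic status are not. The wording of the participation criterion is an ambiguity, not a demonstrated error. Nothing in the Protocol shows how many such subjects there are or whether they differ by country. Severity is low to moderate, and the case for acting rests on how cheap the remedy is.

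**What to change.** In section 9.3.2.1, and in the pre-initiation window of section 9.7.2, omit from baseline any lipid value taken on, or within 12 weeks after the last dose of, any PCSK9 inhibitor. The interval is borrowed from the Protocol's own exclusion. The Protocol does not call it a washout, so the text should say that it is adopted as a convention. The start and stop dates of other lipid-modifying therapy are already collected and identify most affected values. Report the number of subjects affected by country, and show the baseline mean with and without these values. If the SAP already contains such a rule, the Protocol need only be aligned with it.

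State that the first criterion in section 9.2.3.2 means participation at any time within the 12 weeks, and flag enrolled subjects who fail it where this is known. Enrolment was expected to end in Q4 2018 and Amendment 2 is dated 20 December 2018, so this serves interpretation and flagging more than future recruitment. Appendix C lists no separate item for earlier trial participation, so the flag may be incomplete.

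Cost: a few subjects lose a baseline value, and because no imputation is planned, those left with none drop out of the baseline mean. Even if 10% of 130 were lost, N = 117 gives 98 / √117 = 9.06 mg/dL instead of 8.60.
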